8.1 Disposition of Subjects

Disposition data from each study will be integrated, listed, and summarized for the Safety population.

A frequency table by treatment/analysis group and overall will include the number and percentage of subjects along with last available completion status.

A separate table will show the number (%) of subjects who withdrew and the primary reason for withdrawal, by treatment/analysis group and overall. The primary reasons of withdrawal reported by subjects will be presented in this table. The number (%) of subjects who discontinued study drug and the reason for early discontinuation will be summarized in a

separate table. Subjects may contribute more than one event to the summary table since it is possible for a subject to discontinue from more than one study. A footnote indicating the number of subjects with multiple study discontinuations will be included in the summary table.

The time to discontinuation of study drug will be analyzed. The time to discontinuation is defined as the number of days from the Analysis Day 1 date to the last dose of study drug for a particular treatment. Subjects will be censored if no early study drug discontinuation occurred. The median duration and the associated 95% confidence interval for each treatment group will be estimated using the Kaplan-Meier method (log-log transformation). Kaplan-Meier estimates of the survival function will be calculated and displayed graphically.

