8.8 Treatment Compliance

Treatment compliance data will not be integrated. Summaries are provided in the individual study results.

9 Safety Analysis

Safety endpoints will be summarized using integrated data by treatment/analysis group from the time of first dose and include all available safety data. No formal statistical testing is planned.

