9.2.8 Adverse Events of Special Interest

Adverse events of special interest are grouped into three event categories: Neuropsychiatric (CNS), Falls, and Hallucinations. The CNS category combines the following SOCs: Nervous system disorder and Psychiatric disorder. The Falls category combines all PTs that contain the term "Fall" or "Falls". The Hallucinations category combines all PTs that contain the term "Hallucination".

Event incidence will be summarized treatment/analysis group.

Time to onset will be analyzed and is defined as the number of days from the first dose of study drug to the onset of the first AE in the category. Subjects will be censored at the latest date known not to have had such AE. The median time to event and the associated 95% confidence interval for the Placebo and 340 mg ADS-5102 treatment groups will be estimated using the Kaplan-Meier method. Kaplan-Meier estimates of the survival function will be calculated and displayed graphically.

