xxxxx-xx-xxx	XXXXX	340mg ADS-5102	XXXXXXXXXXXXXXXXXXXXXXXXXXXXXXXXXXXXXX	DDMMMYYYY (xx)/ DDMMMYYYY (xx)/ XX	Moderate/ Related/ Recovered/Resolved with sequelae/ Drug Interrupted
xxxxx-xx-xxx	XXXXX	340mg ADS-5102	XXXXXXXXXXXXXXXXXXXXXXXXXXXXXXXXXXXXXX	DDMMMYYYY (xx)/ DDMMMYYYY (xx)/ XX	Severe/ Not Related/ Unknown/ Drug Withdrawn
xxxxx-xx-xxx	XXXXX	260mg ADS-5102	XXXXXXXXXXXXXXXXX/ XXXXXXXXXXXXXXXX/ XXXXXX	DDMMMYYYY (xx)/ DDMMMYYYY (xx)/ XX	Mild/ Related/ Not Recovered/Not resolved/ Other
XXXXX-XX-XXX	XXXXX	340mg ADS-5102	XXXXXXXXXXXXXXXXXXXXXXXXXXXXXXXXXXXXXX	DDMMMYYYY (xx)/ DDMMMYYYY (xx)/ XX	Severe/ Not Related/ Fatal/ Dose not changed

¹Duration (Days) = Stop date - Start date + 1.

Source Data: Listing 2.6.1

<DIRECTORY PATH>PROGRAM NAME Executed: DDMMMYYYY hh:mm

Adverse Events Leading to Study Drug Discontinuation, by System Organ Class and Preferred Term Safety Population

Same display as 1.6.2.1

Note: A subject is counted once within each preferred term and system organ class. Percentages are calculated out of the number of subjects in each treatment/analysis group. AEs are coded using MedDRA Version 17.0.

Source Data: Listing 2.6.3

<DIRECTORY PATH>PROGRAM NAME Executed: DDMMMYYYY hh:mm

Table 1.6.8

Adverse Events Leading to Study Drug Dose Reduction, by System Organ Class and Preferred Term Safety Population

Same display as 1.6.2.1

Note: A subject is counted once within each preferred term and system organ class. Percentages are calculated out of the number of subjects in each treatment/analysis group. AEs are coded using MedDRA Version 17.0.

Source Data: Listing 2.6.3

Table 1.6.9 Listing of Adverse Events Leading to Death Safety Population

Same display as 1.6.6, with outcome "Death".

¹Dur = Duration (Days = Stop date - Start date + 1). Source Data: Listing 2.6.1

Table 1.6.10.1
Incidence of AE (Neuropsychiatric)
Safety Population

System Organ Class		340mg	≥340mg	
Preferred Term	Placebo	ADS-5102	ADS-5102	ADS-5102
Number of AE (Neuropsychiatric) events	XX	XX	XX	XX
System Organ Class 1	XX	XX	XX	XX
Preferred Term 1	xx	XX	XX	XX
Preferred Term 2	xx	XX	XX	XX
Preferred Term 3	xx	XX	XX	XX
	XX	XX	XX	XX
	xx	XX	XX	XX
System Organ Class 2	xx	XX	XX	XX
Preferred Term 1	xx	XX	XX	XX
Preferred Term 2	XX	XX	XX	XX
Preferred Term 3	xx	XX	XX	XX

Note: The Neuropsychiatric category combines the following System Organ Classes: Nervous system disorder and Psychiatric disorder. AEs are coded using MedDRA Version 17.0.

Source Data: Listing 2.6.1

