Table 1.6.10.2

Kaplan-Meier Analysis of Time to Onset of AE (Neuropsychiatric)

Safety Population

	Placebo	340 mg ADS-5102
	(N=xx)	(N=xx)
Days to onset of first AE: Neuropsychiatric		
Event n(%)	xx (xx.x)	xx (xx.x)
10th percentile (days)	XX.X	XX.X
25 th percentile (days)	XX.X	XX.X
50th percentile (days)	XX.X	XX.X
75 th percentile (days)	XX.X	XX.X
90th percentile (days)	XX.X	XX.X
Min - Max	xx.x - xx.x	xx.x - xx.x
edian (days)		
Estimate	XX.X	XX.X
95% CI	x.xx, x.xx	x.xx, x.xx

Note: Percentages are calculated out of the number of subjects in each treatment group. "+" in MIN - MAX means censored value. AEs are coded using MedDRA Version 17.0. NE = Non-estimable.

Note: The Neuropsychiatric category combines the following System of Organs: Nervous system disorder and Psychiatric disorder. Subjects will be censored at their last contact date if no AE (Neuropsychiatric) occurred.

Source Data: Listing 2.6.1

<DIRECTORY PATH>PROGRAM NAME Executed: DDMMMYYYY hh:mm

Programming Note: Some percentiles will be non-estimable. When this occurs, use " NE^{1} "

Table 1.6.10.3

Kaplan-Meier Analysis of Time to Onset of AE (Neuropsychiatric) by Gender Safety Population

	Placebo	340 mg ADS-5102
	(N=xx)	(N=xx)
Days to onset of first AE: Neuropsychiatric		
Event n(%)	xx (xx.x)	xx (xx.x)
10th percentile (days)	XX.X	xx.x
25 th percentile (days)	XX.X	xx.x
50th percentile (days)	XX.X	xx.x
75 th percentile (days)	XX.X	xx.x
90 th percentile (days)	XX.X	XX.X
Min - Max	xx.x - xx.x	xx.x - xx.x
Median (days)		
Estimate	XX.X	XX.X
95% CI	X.XX, X.XX	x.xx, x.xx

Note: Percentages are calculated out of the number of subjects in each treatment group. "+" in MIN - MAX means censored value. AEs are coded using MedDRA Version 17.0. NE = Non-estimable.

Note: The Neuropsychiatric category combines the following System of Organs: Nervous system disorder and Psychiatric disorder. Subjects will be censored at their last contact date if no AE (Neuropsychiatric) occurred.

Source Data: Listing 2.6.1

<DIRECTORY PATH>PROGRAM NAME Executed: DDMMMYYYY hh:mm

Programming Note: Some percentiles will be non-estimable. When this occurs, use " NE^{1} "

Gender: Male

Min - Max

340 mg ADS-5102 (N=xx)

> xx (xx.x) xx.x

> > XX.X

XX.X

XX.X

XX.X

xx.x - xx.x

XX.X

XX.X

XX.X

xx.x - xx.x

Table 1.6.10.3

Kaplan-Meier Analysis of Time to Onset of AE (Neuropsychiatric) by Gender Safety Population

	Placebo
	(N=xx)
Days to onset of first AE: Neuropsychiatric	
Event n(%)	xx (xx.x)

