Kaplan-Meier Analysis of Time to Onset of AE (Neuropsychiatric) by Geographic Region Safety Population

Repeat of 1.6.10.3

Geographic Region:

- 1. European Union
- 2. North America

Note: Percentages are calculated out of the number of subjects in each treatment group. "+" in MIN - MAX means censored value. AEs are coded using MedDRA Version 17.0. NE = Non-estimable.

Note: The Neuropsychiatric category combines the following System of Organs: Nervous system disorder and Psychiatric disorder. Subjects will be censored at their last contact date if no AE (Neuropsychiatric) occurred.

Source Data: Listing 2.6.1

Table 1.6.11.1
Incidence of AE (Falls)
Safety Population

Repeat of 1.6.10.1

Note: Percentages are calculated out of the number of subjects in each treatment group. "+" in MIN - MAX means censored value. AEs are coded using MedDRA Version 17.0. NE = Non-estimable.

Note: The Falls category combines all Preferred Terms that contain the terms "Fall" or "Falls". Subjects will be censored at their last contact date if no AE (Falls) occurred.

Source Data: Listing 2.6.1

<DIRECTORY PATH>PROGRAM NAME Executed: DDMMMYYYY hh:mm

Table 1.6.11.2

Kaplan-Meier Analysis of Time to Onset of AE (Falls)

Safety Population

Repeat of 1.6.10.2

Note: Percentages are calculated out of the number of subjects in each treatment group. "+" in MIN - MAX means censored value. AEs are coded using MedDRA Version 17.0. NE = Non-estimable.

Note: The Falls category combines all Preferred Terms that contain the terms "Fall" or "Falls". Subjects will be censored at their last contact date if no AE (Falls) occurred.

Source Data: Listing 2.6.1

<DIRECTORY PATH>PROGRAM NAME Executed: DDMMMYYYY hh:mm

Programming Note: Some percentiles will be non-estimable. When this occurs, use " $NE^{1/7}$

Kaplan-Meier Analysis of Time to Onset of AE (Falls) by Gender Safety Population

Repeat of 1.6.10.3

Gender:

- 1. Female
- 2. Male

Note: Percentages are calculated out of the number of subjects in each treatment group. "+" in MIN - MAX means censored value. AEs are coded using MedDRA Version 17.0. NE = Non-estimable.

Note: The Falls category combines all Preferred Terms that contain the terms "Fall" or "Falls". Subjects will be censored at their last contact date if no AE (Falls) occurred.

Source Data: Listing 2.6.1

<DIRECTORY PATH>PROGRAM NAME Executed: DDMMMYYYY hh:mm

Table 1.6.11.4

Kaplan-Meier Analysis of Time to Onset of AE (Falls) by Age Safety Population

Repeat of 1.6.10.3

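### For falls and hallucinations the only planned 95% CI is on a Kaplan-Meier median that the placebo group will almost never reach if 25-week incidence is below about 40%

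*SAP*

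**What the plan says.** SAP 9.2.8 defines three special-interest categories: neuropsychiatric events, falls and hallucinations. It plans two summaries for each.

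- **Incidence, descriptive only:** "Event incidence will be summarized treatment/analysis group". The shell (Table 1.6.10.1, repeated as 1.6.11.1 and 1.6.12.1) opens with the row "Number of AE (Neuropsychiatric) events" and holds event counts, with no denominator and no interval.
- **Time to first onset:** "The median time to event and the associated 95% confidence interval for the Placebo and 340 mg ADS-5102 treatment groups will be estimated" by Kaplan-Meier, with the curves plotted. The shell (Table 1.6.10.2, repeated as 1.6.11.2 and 1.6.12.2) shows N, a crude number and percentage with an event, the 10th to 90th percentiles, and the median with a 95% CI. Only the median has an interval. The subgroup tables (1.6.11.3-14 and 1.6.12.3-14) follow the same layout.

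The SAP foresees missing entries. Its programming notes say "Some percentiles will be non-estimable" and have them printed as NE. The opening of SAP Section 9 adds: "No formal statistical testing is planned". Section 8.1 and Table 1.1.3 plan the same kind of summary for time to drug discontinuation. Section 8.1 names the log-log transformation; 9.2.8 names none.

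**The concern.** The median suits events that most subjects have during follow-up. If fewer than half do, the planned estimate and its interval are blank, and the output gives no statement of precision for the events that the SAP itself singled out.

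Follow-up makes this worse. Placebo dosing lasted 8 weeks in ADS-PAR-AM201 and 25 weeks in ADS-AMT-PD301. Exposure to 340 mg can continue through ADS-AMT-PD302 for up to 101 more weeks. The two medians therefore need not both exist, or fall where both groups are under observation. The crude percentage beside them mixes 8-week, 25-week and longer follow-up, so it is not a fair comparison between the columns. Safety is the primary objective of ADS-AMT-PD302 and no tests are planned, so intervals are the only formal statement of uncertainty a reader will get.

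**Working it through.** The plan states no precision figure, so there is none to reproduce. The check asks when the planned interval can exist.

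**Inputs from the documents**
- Placebo N: 83 randomized in ADS-PAR-AM201 (SAP 3), less 61 on active drug (Protocol 4.4), gives 22. ADS-AMT-PD301 gives 126/2 = 63. Total about 85.
- Longest contiguous 340 mg dosing: 25 + 101 = 126 weeks.
- Fall and hallucination rates: none given. Protocol 4.4 only names hallucinations among the most frequent events.

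**Step 1. When the limits exist.** The point estimate needs cumulative incidence F of at least 50%. Inverting pointwise 95% limits for the curve, without censoring:

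| N | Lower limit exists from F | Upper limit exists from F |
|---|---|---|
| 85 | 39-40% | 61% |
| 250 (assumed) | 44% | 56% |

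A complete two-sided interval therefore needs incidence well above one half. For placebo to reach its median by Week 25 takes about 1.45 first events per person-year.

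**Step 2. Placebo simulation.** 22 subjects followed for 8 weeks and 63 for 25 weeks; assumed 20% dropout by Week 25 and constant hazard; at least 2,000 runs per setting. Entries are the percentage of runs in which the quantity is estimable.

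| Assumed 25-week incidence | Median | Upper 95% limit of median (log-log) | 10th percentile | 25th percentile |
|---|---|---|---|---|
| 10% | 0 | 0 | 48% | 0.05% |
| 20% | 0 | 0 | 98% | not run |
| 30% | 0.1% | 0 | 100% | 80% |
| 40% | 6.5% | 0.1% | not run | not run |
| 50% | 50% | 2.8% | not run | not run |

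A separate simulation without dropout, indexed by crude incidence, agrees. The median was estimable in 1.2% of runs at crude 30% (mean final Kaplan-Meier incidence 36%) and in 31% at crude 40% (mean 47%).

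**Step 3. 340 mg.** With constant hazard and 25-week incidence p, the median is 25 × ln 2 / (−ln(1 − p)) weeks:
- p = 10%: 17.33/0.1054 = 164 weeks, beyond 126.
- p = 20%: 17.33/0.2231 = 78 weeks.
- p = 30%: 17.33/0.3567 = 49 weeks.

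The last two can be observed, but both lie after Week 25. Estimability depends on the data cut. With N = 250 assumed and p = 20%, the median was reached in 24% of runs for follow-up uniform over 4-70 weeks, 82% for 4-95 weeks and 99.8% for 4-126 weeks.

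**Step 4. What a fixed time would give.** At 10% placebo incidence, the Week-25 Kaplan-Meier estimate had a standard error of about 3.8 points, so a 95% interval of roughly ±7.4 points (1.96 × 3.8). The median is never available in this setting.

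**Step 5. How late a fixed time can be.** SAP 4 analyses ADS-AMT-PD302 at a database freeze, on an unstated date. From the study start in the Group 3 inclusion criteria (14 July 2014) to the SAP date (13 November 2015) is 487 days, about 70 weeks. If the freeze is near the SAP date, the longest contiguous 340 mg follow-up is about 70 + 25 = 95 weeks, and a Week 100 row could have nobody at risk.

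**The case against.** The strongest reply is that this is a descriptive safety summary, that the SAP foresees non-estimable percentiles, and that nothing in it is contradictory or invalid. That is right, and it is why the point is an improvement and not an error. A reader could also form an interval from N and the crude count: 8 of 85 gives an exact 95% CI of 4.2-17.7%. But that interval treats 8-week and 25-week subjects alike, and the 340 mg counterpart pools still longer follow-up.

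Several stronger readings are tempting and are not supported:

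- **That only a crude percentage remains.** The curves and lower percentiles allow for censoring, and the placebo 10th percentile is estimable in 48% of runs at 10% incidence and 98% at 20%. What they lack is a planned interval.
- **That the 340 mg median will also read NE.** At 20% per 25 weeks it may well be reached, depending on the freeze.
- **That falls and hallucinations are known to be minority events.** No rate is given.
- **That the discontinuation median in Table 1.1.3 will be missing.** No discontinuation rate is given.
- **That the neuropsychiatric category fails in the same way.** It covers two whole system organ classes and may reach its median.

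The Kaplan-Meier figures are not reproduced in the available text, so confidence bands on the templates cannot be excluded. The SAP text and table shells plan none.

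**Conclusion.** The point holds for falls and hallucinations, most firmly in the placebo column. If 25-week incidence is below about 40%, the placebo median and its interval will almost always be non-estimable, and a complete interval is rare even at 50%. In the 340 mg column the median may be missing at about 10% or less per 25 weeks. At higher rates it may appear, but possibly at a time when no placebo subject is on treatment, so the two columns would not be comparable. As written, the text and shells plan no usable precision statement and no matched-time comparison.

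This rests on assumed event rates (5-40%), constant hazard, 20% placebo dropout, a placebo N of about 85 derived from the documents, and an assumed 250 subjects on 340 mg. The placebo result depends mainly on the rate; the 340 mg result also depends on the freeze date.

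**What to change.** In SAP 9.2.8 and Tables 1.6.11.2-14 and 1.6.12.2-14:

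- Add Kaplan-Meier cumulative incidence with a 95% CI and number at risk at matched times for Placebo and 340 mg, for example Weeks 4, 8 and 25.
- State that the intervals use the log-log transformation, as Section 8.1 already does.
- Add later times for 340 mg only where enough subjects remain at risk at the database freeze, for example Week 52. Do not include Week 100 by default.
- Keep the percentiles and median as secondary output.

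The same rows may be added to Table 1.1.3 for consistency.

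The cost is SAP wording and a few shell rows. The data and the Kaplan-Meier procedure do not change.

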9.3 Clinical Laboratory Evaluations

Clinical laboratory data for liver and renal function parameters will be integrated, listed, and summarized for the Safety population. Summaries for all other parameters are available in the individual study reports.

Laboratory assessments for these parameters were performed by a central laboratory. All summaries will be based on the SI units provided by the central lab.

Maximum on-treatment values will be summarized for the liver function parameters and minimum on-treatment values will be summarized for the renal function parameters. For both groups, the change from baseline to the maximum/minimum value will be presented.

All clinical laboratory measures will be classified as Low, Normal, or High, or Normal/Abnormal according to the normal ranges. These categorical data will be summarized in shift tables comparing the results at the baseline visit with the most abnormal results over the treatment period.

Liver function parameters include:

- Bilirubin
- Alkaline phosphatase
- γ-glutamyltransferase
- Alanine aminotransferase
- Aspartate aminotransferase

Renal function parameters include:

- Blood urea nitrogen
- Creatinine
- Estimated GFR MDRD-NKDEP
- Estimated GFR Cockcroft-Gault

Estimated GRF – Cockcroft-Gault values are not reported in the individual study databases and will be calculated as follows:

Integrated Summary of Safety for ADS-5102

Date Issued: 13Nov2015

eCreatinine Clearance $(ml/min/1.73 m^2) =$

[1.73 \times (140 – age) \times wt (kg) \times (0.85 if female) / Serum creatinine (mg/dL) \times 72 \times Body Surface Area;

Creatinine in mg/dL is rounded to 1 decimal place prior to applying the Cockcroft-Gault equation.

The equation to calculate Body surface area is described as following:

Body Surface Area(m²) = [weight (kg) \times height (cm)/3600]^{1/2}

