9.4 Vital Sign Measurements

Vital sign measures for systolic blood pressure, diastolic blood pressure, and heart rate will be integrated and listed for the Safety population. All other measurements will not be integrated. Summary tables are available in the individual study results.

Minimum and maximum on-study values and change from baseline will be presented by treatment/analysis group for sitting systolic blood pressure, sitting diastolic blood pressure, and heart rate.

10 References

Goetz, C. G., et al. (2013). "Which Dyskinesia Scale Best Detects Treatment Response?" Movement Disorders 28(3): 341-346

Stokes, M. E., Davis, C. S., and Koch, G. G. (2000), Categorical Data Using the SAS System, Second Edition, Cary, NC: SAS Institute Inc.

Verhagen-Metman, Del Dotto P, Van Den Muckhof, Fang J, Mouradian M, Chase T. Amantadine as treatment for dyskinesias and motor fluctuations in Parkinson's disease. Neurology. 1998; 50(5): 1323-1326.

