Normal	xx (xx.x)	xx (xx.x)	xx (xx.x)	xx (xx.x)	
High	xx (xx.x)	xx (xx.x)	xx (xx.x)	xx (xx.x)	
Missing	xx (xx.x)	xx (xx.x)	xx (xx.x)	xx (xx.x)	

Note: Baseline is defined as last available value prior to ther first dose of study medication for a particular treatment. The worst value is defined as the maximum on-study value. High = Higher than the upper limit of the normal range, Low = Lower than the lower limit of the normal range, Normal = within the lower and upper limits of the normal range. Percentages are based on the number of subjects in each treatment/analysis group.

Source Data: Listing 2.7.1

Table 1.7.2.1
Renal Function Tests
Safety Population

Repeat of 1.7.1.1

Note: Baseline is defined as last available value prior to ther first dose of study medication for a particular treatment.

¹Change from baseline: post-baseline value - baseline value. For the change from baseline, only subjects with a value at both the baseline visit and the specific post-baseline visit are included. Source Data: Listing 2.7.2

<DIRECTORY PATH>PROGRAM NAME Executed: DDMMMYYYY hh:mm

Parameters: Blood Urea Nitrogen, Creatinine, Estimated GFR - MDRD, Estimated GFR - Cockcroft-Gault

Table 1.7.2.2

Renal Function Tests - Shifts from Baseline to Worst On-Study Value
Safety Population

Repeat of 1.7.1.2

Source Data: Listing 2.7.2

Note: Baseline is defined as last available value prior to ther first dose of study medication for a particular treatment. The worst value is defined as the minimum on-study value. High = Higher than the upper limit of the normal range, Low = Lower than the lower limit of the normal range, Normal = within the lower and upper limits of the normal range. Percentages are based on the number of subjects in each treatment/analysis group.

Table 1.8
Vital Signs
Safety Population

Parameter: XXXXX (units)

·	·	340mg	≥340mg	
	Placebo	Placebo ADS-5102		ADS-5102
	(N=xx)	(N=xx)	(N=xx)	(N=XX)
Baseline				
n	XX	xx	xx	XX
Mean	XX.X	XX.X	xx.x	XX.X
SD	XX.XX	xx.xx	xx.xx	XX.XX
Median	XX.X	xx.x	xx.x	XX.X
Min, Max	XX, XX	XX, XX	XX, XX	XX, XX
linimum				
n	XX	xx	xx	XX
Mean	XX.X	XX.X	XX.X	XX.X
SD	XX.XX	XX.XX	XX.XX	XX.XX
Median	XX.X	XX.X	XX.X	XX.X
Min, Max	XX, XX	XX, XX	XX, XX	xx, xx
Maximum				
n	XX	xx	xx	XX
Mean	XX.X	XX.X	XX.X	XX.X
SD	xx.xx	xx.xx	xx.xx	XX.XX
Median	XX.X	XX.X	XX.X	XX.X
Min, Max	xx, xx	xx, xx	xx, xx	XX, XX

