Adverse Events Leading to Study Drug Discontinuation
Safety Population

Same layout as X.X

¹Duration (Days = Stop date - Start date + 1). Adverse events are coded using MedDRA Version 17.0.

<DIRECTORY PATH>PROGRAM NAME Executed: DDMMMYYYY hh:mm

Listing 2.7.1
Laboratory Results - Liver Function Tests
Safety Population

Subject Identifier	Study Identifier	Treatment	Sample Date	Laboratory Test	Result	Units	Flag	Normal Range
XXXXX-XX-X-XXX	XXXXX	260mg ADS-5102	DDMMMYYYY	XXXXXXXXXXXXXXX	XXX.X	XXXXX		XXX.X-XXX.X
				XXXXXXXXXXXXXX	XXX.X	XXXXX		XXX.X-XXX.X
			DDMMMYYYY	XXXXXXXXXXXXXX	XXX.X	XXXXX	L*	XXX.X-XXX.X
				XXXXXXXXXXXXX	XXX.X	XXXXX		XXX.X-XXX.X
	XXXXX	340mg ADS-5102	DDMMMYYYY	xxxxxxxxxxxx	XXX.X	XXXXX	Н	XXX.X-XXX.X
				XXXXXXXXXXXXXX	XXX.X	XXXXX	Н	XXX.X-XXX.X
			DDMMMYYYY	XXXXXXXXXXXXXX	XXX.X	XXXXX		XXX.X-XXX.X
				XXXXXXXXXXXXXX	XXX.X	XXXXX		XXX.X-XXX.X

Note: H = Above Normal Range, L = Below Normal Range, N = Normal, * indicates minimum value

<DIRECTORY PATH>PROGRAM NAME Executed: DDMMMYYYY hh:mm

Listing 2.7.2

Laboratory Results - Renal Function Tests
Safety Population

Same as X.X

Listing 2.8
Vital Sign Results
Safety Population

Subject Identifier				Blood Pressure(mmHg)				
	Study Identifier	Treatment	Test Date	Sitting Systolic/Diastolic	Standing Systolic/Diastolic	Heart Rate (bpm)	Height (cm)	Weight (kg)
XXXXX-XX-X-XXX	XXXXX	260mg ADS-5102	DDMMMYYYY DDMMMYYYY	xx/xx xx/xx	xx/xx	xxx xxx	XXX.X	XX.X
		340mg ADS-5102	DDMMMYYYY	xx/xx	xx/xx	XXX	XXX.X	XX.X

[figure not shown]
Heart Rate (bpm=beats/minute)

ADS-5102 Integrated Summary of Safety

- Figure 3.1 Kaplan-Meier Analysis of Time to Study Drug Discontinuation Safety Population
- Figure 3.6.1.1 Kaplan-Meier Analysis of Time to Onset of AE (Neuropsychiatric) Safety Population
- Figure 3.6.1.2 Kaplan-Meier Analysis of Time to Onset of AE (Neuropsychiatric) by Gender Safety Population
- Figure 3.6.1.3 Kaplan-Meier Analysis of Time to Onset of AE (Neuropsychiatric) by Age Safety Population
- Figure 3.6.1.4 Kaplan-Meier Analysis of Time to Onset of AE (Neuropsychiatric) by Race Safety Population
- Figure 3.6.1.5 Kaplan-Meier Analysis of Time to Onset of AE (Neuropsychiatric) by Baseline Renal Function Safety Population
- Figure 3.6.1.6 Kaplan-Meier Analysis of Time to Onset of AE (Neuropsychiatric) by Weight Safety Population
- Figure 3.6.1.7 Kaplan-Meier Analysis of Time to Onset of AE (Neuropsychiatric) by Baseline MAO-B Inhibitor Medications Safety Population

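### The SAP takes the on-treatment minimum as the worst value for all four renal parameters; for creatinine and BUN that is the best value

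*SAP*

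**What the plan says.** SAP section 9.3 assigns the maximum to the liver parameters and then states that "minimum on-treatment values will be summarized for the renal function parameters". It adds: "For both groups, the change from baseline to the maximum/minimum value will be presented". The renal group has four members and no exception is made for any of them. The shell for Table 1.7.2.1 repeats the list: "Parameters: Blood Urea Nitrogen, Creatinine, Estimated GFR - MDRD, Estimated GFR - Cockcroft-Gault".

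The note to the renal shift table (Table 1.7.2.2) applies the same rule: "The worst value is defined as the minimum on-study value".

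Other parts of the SAP do not fit this rule:

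- The shift-table sentence in section 9.3 says the categories will be "summarized in shift tables comparing the results at the baseline visit with the most abnormal results over the treatment period", with no direction given.
- The shell for Table 1.7.2.1 is given as "Repeat of 1.7.1.1". That is the liver table, whose post-baseline row is headed *Maximum*.
- The footnote to Listing 2.7.1 (liver) reads "L = Below Normal Range, N = Normal, * indicates minimum value", although section 9.3 uses the maximum for liver. Listing 2.7.2 (renal) has only a placeholder cross-reference.

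For vital signs, section 9.4 takes a different approach: "Minimum and maximum on-study values and change from baseline will be presented by treatment/analysis group".

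**The concern.** The four renal parameters do not share an adverse direction. The protocol's renal concern is a fall in eGFR: section 6.4 acts on confirmed values below 50 and below 30 mL/min/1.73m². A fall in eGFR means a rise in creatinine. The minimum is therefore right for the two eGFR estimates and wrong for creatinine. It is also wrong for BUN, where a rise is the usual sign of worse renal function; that is general clinical knowledge, not something the documents state.

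Under the written rule, the creatinine and BUN summaries, changes from baseline and shifts would show each subject's best on-treatment result, labelled worst in the shift table. A transient or late rise would disappear, and a rise present at every visit would be understated. One table could show eGFR falling beside creatinine that does not rise. The shell conflicts add to the problem, because neither a single minimum nor a single maximum suits all four parameters.

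**Working it through.** The plan states no figure on this point, so there is none to reproduce. The check covers direction first, then the consequence of the rule.

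**Inputs from the documents.** The rule and parameter list come from SAP 9.3 and the notes to Tables 1.7.2.1 and 1.7.2.2. The Cockcroft-Gault and body-surface-area (BSA) formulas come from SAP 9.3. Protocol Table 6 gives ten on-treatment chemistry draws in ADS-AMT-PD302 (Weeks 4, 8, 16, 28, 40, 52, 64, 76, 88 and 100).

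**Assumptions, not in the documents.** Baseline creatinine 0.9 mg/dL, upper limit of normal 1.2 mg/dL, within-subject CV 8%, normal and independent variation between visits, and 2 to 10 on-treatment draws.

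**1. Direction, by the SAP's own formula.**

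Clearance = 1.73 × (140 − age) × weight × (0.85 if female) / (creatinine × 72 × BSA), with BSA = √(weight × height / 3600).

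Take an illustrative man aged 70, 75 kg, 170 cm. BSA = √(75 × 170 / 3600) = 1.882, and 1.73 × 70 × 75 = 9082.5. Clearance is therefore 9082.5 / (72 × 1.882 × creatinine) = 67.03 / creatinine.

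| | Baseline | Draw 1 | Draw 2 | Draw 3 | Draw 4 | Draw 5 |
|---|---|---|---|---|---|---|
| Creatinine (mg/dL) | 0.9 | 0.9 | 1.0 | 1.6 | 1.1 | 0.8 |
| Clearance (mL/min/1.73m²) | 74.5 | 74.5 | 67.0 | 41.9 | 60.9 | 83.8 |

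The minimum rule reports a clearance of 41.9, a clear decline from 74.5. For the same subject it reports a worst creatinine of 0.8, a change of −0.1. That creatinine belongs to his best clearance, 83.8. The maximum creatinine, 1.6 (change +0.7), is the one that goes with 41.9.

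**2. Bias with no drug effect.** The expected minimum of k independent normal values lies c SDs below the subject's mean, with c = 0.564, 1.163 and 1.539 for k = 2, 5 and 10. At 8% CV the mean change to the minimum is −0.564 × 8% = −4.5%, −1.163 × 8% = −9.3% and −1.539 × 8% = −12.3%. In SD units the result holds equally for BUN. The apparent improvement grows with the number of draws.

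**3. Mean change with a true 30% rise** (simulated; SD proportional to level):

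| Pattern | 2 draws: to minimum / to maximum | 10 draws: to minimum / to maximum |
|---|---|---|
| No effect | −4.5% / +4.5% | −12.3% / +12.3% |
| Rise at one visit | about 0% / +30% | −11.9% / +30.3% |
| Rise in second half of visits | about 0% / +30% | −9.3% / +42.1% |
| Rise at every visit | +24.1% / +35.9% | +14.0% / +46.0% |

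**4. Shift to High with a true 50% rise.** The raised mean is 1.35 and its SD is 0.08 × 1.35 = 0.108. A raised visit exceeds 1.2 with probability Φ((1.35 − 1.20) / 0.108) = Φ(1.39) = 0.918. An unaffected visit exceeds 1.2 with probability of about 0.00002.

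- Rise at one visit: practically 0% by the minimum, about 92% by the maximum.
- Rise at every visit, 2 draws: 0.918² = 84% by the minimum, 1 − 0.082² = 99% by the maximum.
- Rise at every visit, 10 draws: 0.918¹⁰ = 42% by the minimum, 100% by the maximum.

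Without any assumed value: under the minimum rule a subject is classed as High only if every on-treatment value is High. This holds for BUN as for creatinine. The shift figures apply if the Table 1.7.2.2 note governs; the section 9.3 shift sentence, read alone, would pick up a High value.

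**The case against.** The strongest reply is that little creatinine information is lost. The SAP's formula makes Cockcroft-Gault inversely proportional to creatinine, apart from rounding and small changes in age and weight, so the eGFR minimum row carries the creatinine maximum in the same table. Table 1.1.2 has rows for discontinuation at eGFR below 50 and below 30. Protocol section 12.3 has clinically significant laboratory findings recorded as adverse events. The laboratory listing layout flags High values individually, and protocol section 13.1.4 plans visit-level laboratory summaries for PD302. SAP section 9 plans no formal testing, and no dosing or stopping rule uses these rows. All of this stands and limits the consequence. It does not make the creatinine rows correct, and BUN has no mirror in the summary tables.

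A second reply is that the SAP is inconsistent rather than wrong. The shift sentence in 9.3 would pick up a High creatinine, and the literal Table 1.7.2.1 shell would give the right extreme for creatinine and BUN. But the two explicit statements of direction both say minimum. The shell's *Maximum* row may be only a layout instruction and, taken literally, would be wrong for both eGFR estimates. No reading gives the right extreme for all four parameters throughout.

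A third reply is that the sizes are illustrative. That is fair: the variability, limits and patterns are assumed. PD302 is analysed at a database freeze, so many subjects may have fewer than ten draws. Gap-free rollover subjects on 340 mg keep their earlier baseline (SAP 7.6), so theirs may include draws from the preceding study. The listing footnotes are unfinished shell text, and the vital-signs comparison is a side point.

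**Conclusion.** The concern holds. As written, the SAP reports the most favourable on-treatment creatinine and BUN as the summary extreme, and its shift-table note calls that value the worst. The direction for creatinine follows from the SAP's own formula; for BUN it rests on general clinical knowledge.

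Under the stated assumptions, transient rises vanish and late rises appear as no change or a fall. A sustained 30% rise shrinks to between +24% (2 draws) and +14% (10 draws). The bias grows with the number of draws, so longer-followed ADS-5102 subjects would tend to look better than placebo subjects with shorter follow-up.

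The reach is limited to the creatinine and BUN summaries, changes and shifts in the integrated summary of safety. The eGFR rows are correctly directed by the section 9.3 rule, and PD302's own visit-level summaries are not shown to be affected. This should be fixed, but it does not hide renal decline from the submission as a whole.

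**What to change.** Define the worst on-treatment value by parameter in SAP section 9.3: maximum for BUN and creatinine, minimum for eGFR by MDRD and by Cockcroft-Gault. Then:

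- Give Table 1.7.2.1 its own row label by parameter instead of inheriting *Maximum* from the liver shell.
- Restate the Table 1.7.2.2 note by parameter, so that it agrees with the section 9.3 shift sentence, and use one term throughout (section 9.3 says on-treatment, the note says on-study).
- Correct the extreme-value flag in Listing 2.7.1, define the one in Listing 2.7.2, and replace the placeholder reference there.

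The cost is a sentence in section 9.3, two table shells or notes, two listing footers and a few lines of code. No new data are needed.

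There is one downside. A maximum collects upward noise: with no drug effect and 8% CV, about +4.5% with 2 draws and +12% with 10. The creatinine and BUN rows should therefore be read against placebo. Placebo exposure is 8 weeks in ADS-PAR-AM201 or 25 weeks in ADS-AMT-PD301, against up to 101 weeks of ADS-5102 in PD302, so a footnote on unequal follow-up would help.
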